#### 4.1.1. Dose Finding and Stopping Rules

The Sponsor will make the final decision of doses for the cohorts, including recommendation to repeat a dose or opening enrollment of the subsequent cohort. The E-DMC approval of the Sponsor's recommendation to repeat a dose or opening enrollment of the subsequent cohort will be independently assessed for each of the different age groups and will be based on the safety/tolerability and concentration data.

Repeat dosing at the assessed dose level or progression to the higher dose level will not occur if:

- Mean  $C_{max}$  **CCI** ng/mL and Mean  $AUC_{24}$  **CCI** ng•h/mL, within an age band (**CCI**)

Dosing or enrollment interruption will occur if any of the following is observed:

- Death of a participant during participation in the study receiving study intervention (sisunatovir) and assessed as possibly, probably, or definitely related to study intervention (sisunatovir) by the Investigator(s) and/or Sponsor.
- Two or more SAEs in the same SOC in the study receiving study intervention (sisunatovir) assessed as possibly, probably, or definitely related to study intervention (sisunatovir) by the Investigator(s) and/or Sponsor.
- Severe nonserious AEs, considered as, at least, possibly related to study intervention (sisunatovir), in 2 participants (receiving sisunatovir), independent of within or not within the same organ class, indicating dose limiting intolerance.
- Two or more participants receiving study intervention (sisunatovir) experience the same or a similar AE that is assessed as severe in intensity and in the opinion of the E-DMC and/or Sponsor, represent an unacceptable risk to participants enrolled in the trial.
- If two or more participants receiving study intervention (sisunatovir) develop similar clinically significant laboratory, or vital sign abnormalities, in the same organ class, indicating dose limiting intolerance.

If any of the above criteria are fulfilled, restart of dosing will only be possible if agreed by the E-DMC. Should a clear non-IMP cause for any of the above be identified, the study may continue.

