#### 7.1.2. Liver Injury

A participant who meets the criteria of potential DILI (Hy's law) case as described in [Appendix 5](#) in Section [10.5](#) or if they meet either of the below criteria, will be withdrawn from study intervention.

- Participants >30 days old with finding of pre-dose AST, ALT or T bili >2 × ULN;
- Any participant during study intervention with at least 2 of the following labs AST, ALT or T bili increase by >2 ULN.

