#### 7.1.3. ECG Changes

A participant who meets either bulleted criterion will be withdrawn from the study intervention.

- QTcF >500 ms.
- Change from baseline: QTcF  $\geq$  60 ms

If a clinically significant finding is identified (including, but not limited to, changes from baseline in QTcF after enrollment), the investigator or qualified designee will determine if the participant can continue in the study and if any change in participant management is needed. This review of the ECG printed at the time of collection must be documented. Any new clinically relevant finding should be reported as an AE.

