### 10.3. Appendix 3: Adverse Events: Definitions and Procedures for Recording, Evaluating, Follow-Up, and Reporting

#### 10.3.1. Definition of AE

| AE Definition   |
|---|
| 

• An AE is any untoward medical occurrence in a patient or clinical study participant, temporally associated with the use of study intervention, whether or not considered related to the study intervention.

• Note: An AE can therefore be any unfavorable and unintended sign (including an abnormal laboratory finding), symptom, or disease (new or exacerbated) temporally associated with the use of study intervention.

 |

| Events Meeting the AE Definition  |
|--|
| 

• Any abnormal laboratory test results (hematology, clinical chemistry, or urinalysis) or other safety assessments (eg, ECG, radiological scans, vital sign measurements), including those that worsen from baseline, considered clinically significant in the medical and scientific judgment of the investigator. Any abnormal test results that meet any of the conditions below must be recorded as an AE:

• Is associated with accompanying symptoms.

• Requires additional diagnostic testing or medical/surgical intervention.

• Leads to a change in study dosing (outside of any protocol-specified dose adjustments) or discontinuation from the study, significant additional concomitant drug treatment, or other therapy.

• Exacerbation of a chronic or intermittent preexisting condition, including an increase in either frequency and/or intensity of the condition.

• New condition detected or diagnosed after study intervention administration, even though it may have been present before the start of the study.

• Signs, symptoms, or the clinical sequelae of a suspected drug-drug interaction.

• Signs, symptoms, or the clinical sequelae of a suspected overdose of either study intervention or a concomitant medication. Overdose per se will not be reported as an AE or SAE unless it is an intentional overdose taken with possible suicidal/self-harming intent. Such overdoses should be reported regardless of sequelae.

 |

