## Monitoring and Discontinuation Criteria for All Cohorts

| Potential Criteria       | Recommendations  |
|--------------------------|--|
| Monitoring Criteria      | 
Neonates < 28 days old:
(i) Screat increase <math>\geq 0.3</math> mg/dL (<math>\geq 26.5</math> <math>\mu</math>mol/L) within 48 hours OR
(ii) Screat increase <math>\geq 1.5</math> to 1.9 times from baseline (previous lowest value) known or suspected to have occurred within the prior 7 days
 
Infants and children <math>\geq 28</math> days old and < 12 years old:
(i) Screat increase <math>\geq 0.3</math> mg/dL (<math>\geq 26.5</math> <math>\mu</math>mol/L) within 48 hours OR
(ii) Screat increase <math>\geq 1.5</math> times baseline known or suspected to have occurred within the prior 7 days
 |
| Discontinuation Criteria | 

Two sequential increases in serum creatinine that confirm the above changes over the screening or baseline value as indicated in the monitoring criteria.

Note: If the serum creatinine increases may be caused by an identifiable and reversible reason (eg, concomitant medication), then an additional retest may be allowed after discussion with the medical monitor. After retest, a decision for the subject to continue in the study will be made after discussion with the medical monitor.

   |

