3.1.3.2. Vital signs

Vital signs measures will include blood pressure (BP), pulse rate (PR), Temperature (Tympanic, Rectal or Skin), respiratory rate (RR) and Oxygen saturation (SpO₂). Baseline will be the last pre-dose measurement.

At times defined in the protocol SoA, a single measurement of BP and PR will be assessed with a completely automated device.

Temperature and the highest respiratory rate at the time of assessment will be recorded.

Oxygen saturation findings collected during the study will be recorded on the CRF including any supplemental O₂ requirement. The lowest SpO₂ value, while on room air at the time of assessment will be documented.

The following endpoints will be determined:

- Change from baseline in systolic and diastolic BP, pulse rate, temperature, respiratory rate, and SpO₂.
- The minimum and maximum post-dose systolic and diastolic BP, pulse rate, temperature, respiratory rate, and SpO₂.
- The maximum increase and decrease from baseline over all measurements taken post-dose for systolic and diastolic BP, pulse rate, temperature, respiratory rate, and SpO₂ values.

The maximum increase from baseline will be calculated by selecting the maximum CFB over the respective period, except in the case where a participant does not show an increase. In such an instance, the minimum decrease should be taken. Similarly, the maximum decrease from baseline will be determined by selecting the minimum value of the CFB. In cases where a participant does not show a decrease, the minimum increase should be taken.

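### The Section 4.1.1 interruption criteria leave out ECG findings, so two nonserious, non-severe QTcF withdrawals meet none of them

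*Protocol*

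**What the plan says.** Protocol Section 4.1.1 opens its list with "Dosing or enrollment interruption will occur if any of the following is observed". Five criteria follow, and after any of them "restart of dosing will only be possible if agreed by the E-DMC". The study may continue if a clear cause other than the study drug is found. The fifth criterion applies when two or more participants on sisunatovir "develop similar clinically significant laboratory, or vital sign abnormalities, in the same organ class, indicating dose limiting intolerance".

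Three other places set organ-specific limits for taking an individual child off study drug:

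- **ECG (Section 7.1.3):** QTcF above 500 ms, or a change from baseline of 60 ms or more. "A participant who meets either bulleted criterion will be withdrawn from the study intervention".
- **Liver (Section 7.1.2):** besides a pre-dose limit and potential Hy's law cases, "Any participant during study intervention with at least 2 of the following labs AST, ALT or T bili increase by >2 ULN".
- **Kidney (Appendix 6):** "Two sequential increases in serum creatinine that confirm the above changes over the screening or baseline value as indicated in the monitoring criteria", with a further retest possible when a reversible cause is identified.

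Separately, Section 4.1 obliges the sponsor to halt all randomizations if there is a safety signal of concern, until the E-DMC has reviewed it and recommended continuing. The term is not defined. An earlier E-DMC meeting can also be called.

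**The concern.** A QTcF finding that is enough to stop one child's treatment has no counterpart in the list of cohort-level triggers when it occurs in two children, unless it is also graded severe or classed as serious. Liver and creatinine findings do have a possible route through the fifth criterion.

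What is at stake is timing. The E-DMC reviews unblinded safety data for each cohort, so it would see the events. Until that review, Cohorts 1A, 1B and 1C can enrol concurrently (Section 1.2). Treatment lasts 5 or 6 days and the affected children would already be off drug, so the exposure concerned is mainly that of children enrolled in the interval. Section 2.3.1 names cardiovascular effects as a potential risk and relies partly on event-driven ECGs to mitigate it. Section 4.2 says that part of this population has not been studied before.

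**Working it through.** No figure in the plan is at issue, so the check sets the texts side by side.

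**Step 1: the test case.** Two children on sisunatovir are withdrawn under Section 7.1.3, and neither event is serious or graded severe. The protocol allows this case. Appendix 7 says that a new QTcF above 480 ms or a rise of at least 60 ms may be an AE, and that a value above 500 ms may be an SAE. Neither classification is compulsory. Appendix 3 defines severe by disruption of daily activities, a significant effect on clinical status, or possible need for intensive treatment. A silent QTcF rise in an infant need not meet that definition.

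**Step 2: the five criteria applied to it.**

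| Section 4.1.1 criterion | Requires | Met? |
|---|---|---|
| 1 | A related death | No |
| 2 | Two or more related SAEs in one SOC | No, not serious |
| 3 | Severe, at least possibly related nonserious AEs in 2 participants | No, not severe |
| 4 | The same or a similar severe AE in two or more participants, judged an unacceptable risk | No, not severe |
| 5 | Similar laboratory or vital sign abnormalities in two or more participants | No, see step 3 |

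None of the five is met.

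**Step 3: does ECG count as a laboratory or vital sign finding?** The documents keep it apart from both. Appendix 3 names laboratory results first and then adds "or other safety assessments (eg, ECG, radiological scans, vital sign measurements), including those that worsen from baseline", which lists ECG and vital signs as separate items. The protocol gives vital signs and ECGs separate sections (8.3.2 and 8.3.3). SAP Section 3.1.3.2 states: "Vital signs measures will include blood pressure (BP), pulse rate (PR), Temperature (Tympanic, Rectal or Skin), respiratory rate (RR) and Oxygen saturation". No ECG interval is included.

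**Step 4: the comparison with liver and kidney.** AST, ALT, total bilirubin and serum creatinine are laboratory measures, so on-treatment withdrawals on these grounds fall in the class that the fifth criterion names. They do not trigger it automatically, because the abnormalities must also be clinically significant and indicate dose-limiting intolerance. The pre-dose liver limit in Section 7.1.2 fits poorly, since a baseline finding does not develop on drug. The difference is therefore one of eligibility: liver and creatinine findings can be considered under the criterion, and ECG findings cannot.

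**Step 5: what remains outside the list.** The Section 4.1 halt could cover the test case, but it depends on the sponsor judging that there is a signal, and it speaks of randomizations. Section 4.1.1 covers dosing as well as enrollment and makes restart of dosing conditional on E-DMC agreement.

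**The case against.** The strongest reply is that the safeguard already exists. The Section 4.1 halt is mandatory, and Amendment 1 changed it from optional. The sponsor may review unblinded data at any time (Section 6.4.3) and can reclassify an AE as serious (Section 8.4.1.2). Unplanned ECGs go to a central laboratory (Section 8.3.3), and Appendix 7 recommends its listed findings as alerts to the study team. The E-DMC charter is not available here and may define further triggers. This stands. It covers much of the gap, but none of the visible text says that two such cases call for a pause in dosing.

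A second reply is that the omission may be deliberate. The fifth criterion matches the primary endpoint, which covers laboratory values and vital signs and from which Amendment 3 removed ECG because of the thorough QT study. Leaving investigator-selected ECGs out of a counting rule can be defended, and nothing requires every individual limit to have a cohort-level counterpart. This also stands as a possibility. Amendment 3's list of changed sections includes 7.1.3 but not 4.1.1. The documents do not show how the fifth criterion read before Amendment 3, so intent cannot be established either way.

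Two stronger readings are tempting and are not supported:

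- A reader might infer that repeated QTcF prolongation could not stop the trial. The Section 4.1 halt and the E-DMC reviews contradict that.
- A reader might infer that two liver or creatinine withdrawals force a pause while two QTcF withdrawals do not. The first half is wrong, for the reason in step 4.

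**Conclusion.** The point holds as a gap in the Section 4.1.1 list only. Two nonserious, non-severe QTcF withdrawals on sisunatovir meet none of the five criteria, so a pause would depend on grading or on sponsor judgement under Section 4.1.

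The practical weight is low. The Schedule of Activities has no planned ECG after screening, and Sections 2.2.4 and 2.3.1 report no QT signal of clinical concern. The probability cannot be calculated from the documents. The event rate and the share of children who would have an on-treatment ECG are not given, and the allocation ratio is redacted. Any percentage would only restate assumptions. The conclusion rests on the visible text and on reading laboratory and vital sign in the sense that the documents themselves use. It is a minor, optional improvement.

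**What to change.** In the fifth criterion of Section 4.1.1, extend the types of abnormality to laboratory, vital sign, or ECG. Leave the rest of the sentence unchanged, including the judgements on clinical significance and dose-limiting intolerance, and keep the exception for a clear cause other than the study drug.

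Do not add a clause under which two Section 7.1.3 withdrawals count automatically. That would make the rule stricter for QTcF than for liver or kidney findings.

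The cost is a few words in the protocol and a slightly higher chance of a precautionary pause. No new QTcF threshold, additional ECG or SAP change is needed.

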#### 4.2. Scientific Rationale for Study Design

This study is a randomized, double-blind, sponsor-open, placebo-controlled, multicenter study in RSV-infected outpatient and hospitalized neonates, infants, and children, 1 day up to 60 months of age with RSV-LRTI. This is a dose finding study to evaluate the PK, safety, and tolerability of sisunatovir. The current study will provide additional data at ages previously evaluated in C5241003 and will also evaluate a broader pediatric population (CCI [REDACTED] old and children CCI [REDACTED] old) to inform dose selection in future studies. Since children are a vulnerable population, an E-DMC is used in this study to ensure the safety of participants.

The safety and PK of sisunatovir have not been studied to-date in CCI [REDACTED] but this CCI group is noted to be at the CCI [REDACTED] [3,4]. Additionally, expanding the safety and PK information of sisunatovir CCI [REDACTED] to inform future studies can help ensure correct dose regimens to help prevent acute LRTI hospitalization attributed to RSV disease in children less than 5 years old [2].

There are currently no approved RSV antivirals available, and thus no active control can be proposed as comparator. The comparator for this study is participants receiving placebo. Each cohort evaluated in the study will have participants on placebo. The placebo group is required for assessing the safety, tolerability, and palatability of the study intervention. All

participants (including participants receiving placebo) enrolled in the study will receive the SOC.

According to the DDI risk assessment for sisunatovir as described in Section 2.2.2, sisunatovir is a CCI of CCI. For this reason, sensitive CCI are prohibited in this study. Since sisunatovir is a CCI are also prohibited. Lastly, due to potential risk of CCI inhibition, sensitive substrates of these transporters may be administered with caution during treatment period.

#### 4.2.1. Patient Input Into Design

Parental surveys are being conducted to evaluate feasibility of study recruitment, optimize study participation, and collect feedback on how to enhance potential educational materials available for participant's parent(s)/legal guardians.

#### 4.2.2. Diversity of Study Population

Diversity of study population in this protocol applies to sites in the US only. The diversity strategy will include sites with the potential to support the recruitment of diverse pediatric populations. Reasonable attempts will be made to enroll participants that are representative of the patient population that will be treated with sisunatovir in clinical practice. The following strategies may be explored in support of diverse recruitment efforts:

- Selecting sites that have access to diverse pediatric participants
- Creating and completing individual site recruitment plans in collaboration with sites
- Have proactive discussions with investigator sites throughout the enrollment period to assess and reevaluate site specific strategies as needed to best position each site for the most diverse representation enrollment outcomes
- Developing recruitment and retention materials with culturally and linguistically appropriate language and imagery to resonate with underrepresented populations
- Translating all patient-facing materials into US Spanish
- Providing investigators with recruitment materials for both potential participants and other Healthcare Providers
- Educating site staff on the importance of including diverse participants
- Monitor diverse enrollment to identify potential opportunities to include diverse populations

#### 4.2.3. Rationale for Comparator

There are currently no approved RSV antivirals available, and thus no active control can be proposed as comparator. The comparator for this study is participants receiving placebo. Each cohort evaluated in the study will have participants on placebo. The placebo group is required for assessing the safety, tolerability, and palatability of the study intervention.

All participants (including participants receiving placebo) enrolled in the study will receive the SOC. Participants enrolled in the study while in the outpatient setting may continue in the study if hospitalized at investigator discretion. C5241003 study that completed recruitment, was conducted to characterize the PK profile, safety and virologic response to sisunatovir in RSV-infected hospitalized children aged 1 month - 36 months and included an open-label Part A (1.0, 2.0 and 2.5 mg/kg single dose) and double-blind Part B (CCI [REDACTED]; 2.5 mg/kg, 3.5 mg/kg and 5 mg/kg q12h × 5 days). Initial pediatric dose recommendations for Cohort 1A, 1B, and 1C are based on observed concentrations in Study C5241003 with interpolation of predicted exposures, relative to exposure of CCI mg CCI in adults.

